4.4 STATISTICAL ANALYSIS

The primary endpoint will be estimated annually and it will be expressed as absolute and relative numbers. Survival curves free from study endpoint, eventually divided into subgroups according to variables of interest such as gender, age, underlying heart disease, comorbidity and programming mode, will be drawn with Kaplan-Meier method and compared by Log-rank test. Basal and follow-up parameters (clinical, electrocardiographic and echocardiographic) will be compared by χ^2 test or by Fisher test if they are discrete; by T-student test or signed rank test if they are continuous. Every test will be two-tailed and a value of $p>0.05$ will be considered significant.

According to the number of centers involved we expect to recruit at least 500 patients. Considering an annual incidence of the primary endpoint (death from all causes) of 11% according to our experience (Guerra et al. Europace 2015), we expect about 55 events at the first statistical analysis after one year from the start and we expect about 165 events at the end of the follow-up of three years. The statistical analysis will be conducted using the SPSS 21.0 for Windows software (SPSS Inc. Chicago, IL, USA).

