4. OBSERVATIONAL STUDY DESIGN

Multicenter, observational, prospective clinical study. Data from the first 500 patients enrolled in the registry will be used for the present analysis. Please see point #3 of the present protocol for information regarding registry enrollment criteria and data collection.

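### Age is related to survival only through log-rank tests on age groups with no stated cut points, which loses power and leaves the result open to the choice of cut

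*Combined protocol and SAP*

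**What the plan says.** Section 4.4 plans survival curves "eventually divided into subgroups according to variables of interest such as gender, age", and also by heart disease, comorbidity and ICD programming. These curves "will be drawn with Kaplan-Meier method and compared by Log-rank test". The section gives no age cut points, no number of age groups and no rule for choosing them. No Cox or other regression model appears anywhere in the document.

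The case report form (Attachment #3) records birth date in item 0.1 and the start date of the electrical storm in item 2.1, so exact age at the storm is available. Section 3 describes the registry as exploratory and says the sample is large enough for specific subgroup analyses. Section 4.4 also has the primary endpoint estimated every year.

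**The concern.** A log-rank comparison of Kaplan-Meier curves needs groups, so age has to be cut. Cutting treats everyone on one side of the boundary as having the same risk and discards the ordering within each group. If risk rises smoothly with age, the test uses only part of what the deaths say about age. Section 3 relies on the sample being large enough for subgroup work, and grouping gives part of that advantage back.

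There is a second cost. No cut is fixed and mortality is estimated yearly, so the boundary can be settled after curves have been looked at. The conclusion on age, and its nominal p-value, would then depend on that choice.

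**Working it through.** **Inputs from the plan.** The analysis set is 500: "Data from the first 500 patients enrolled in the registry will be used for the present analysis". The annual death rate is 11%. For the first year the plan says "we expect about 55 events at the first statistical analysis after one year from the start", and it expects about 165 deaths at three years (section 4.4). On sidedness, "Every test will be two-tailed". The significance level is taken as 0.05; the inequality in section 4.4 is printed the wrong way round.

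**The plan's event counts.** 500 × 0.11 = 55 and 500 × 0.11 × 3 = 165, so both figures reproduce. Applying 11% a year to survivors instead gives 500 × (1 − 0.89³) = 147.5 deaths. The percentage loss below is the same for either count.

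**Inputs that are assumptions.** The documents give no age distribution, no cut and no power for any subgroup. I assume roughly normal age, a log-hazard linear in age, and an effect that continuous age would detect with 80% power.

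**Information kept by grouping.** The share kept is the between-group variance of age divided by its total variance.

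- Two groups, with a fraction f above the cut: φ(z_f)² / [f(1 − f)]. At the median this is 2/π = 0.637. At the upper quartile it is 0.3178² / 0.1875 = 0.539.
- Tertiles: the outer group means are ±0.3636 / (1/3) = ±1.091 SD, so the share is (2/3) × 1.091² = 0.793.
- Quartiles: the group means are ±1.271 and ±0.325 SD, so the share is 0.5 × 1.271² + 0.5 × 0.325² = 0.861.

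**Power.** 80% power at two-sided 0.05 means an expected z of 1.96 + 0.84 = 2.80. With two groups, power = P(Z > 1.96 − 2.80 × √share). With three or four groups, the overall log-rank test has 2 or 3 degrees of freedom and noncentrality 2.80² × share, which is about 6.2 and 6.8.

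| Grouping of age | Information lost | Power (continuous = 80%) |
|---|---|---|
| Median split | 36% | 61% |
| Upper-quartile split | 46% | 54% |
| Tertiles | 21% | 60% |
| Quartiles | 14% | 57% |

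Tertiles and quartiles keep more information, but the extra degrees of freedom take most of the gain back.

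**In deaths, for a median split.** 165 × 0.637 = 105, and 147.5 × 0.637 = 94. The hazard ratio per SD of age detectable with 80% power is exp(2.80/√165) = 1.24 on the continuous scale against exp(2.80/√105) = 1.31 after the split. With 147.5 deaths it is 1.26 against 1.34.

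**Sensitivity to the age distribution (median split).** The loss is 35.5% for a normal truncated to 18–95 years (mean 65, SD 12), 34.7–38.4% for two left-skewed shapes, 25% for uniform age, and 46% for a heavy-tailed shape (t with 5 df).

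**Sensitivity to the size of the effect (147.5 deaths, median split).** Power is P(Z > 1.96 − log HR × √147.5) for continuous age; after the split, log HR is also multiplied by √0.637. At a hazard ratio per SD of 1.26 this gives 80% against 61%; at 1.4, 98% against 90%; at 1.5, 99.8% against 97.6%.

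**Simulation check.** In 6,000 runs with 500 patients, three years of follow-up and a hazard ratio of 1.244 per SD (about 149 deaths on average), power was 75% for continuous age and 55% for the median split. The information ratio was 0.626, a loss of about 37%. At a hazard ratio of 1.5 per SD the ratio was 0.621.

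**The case against.** **The plan does not call for a median split.** A reader might infer that the planned analysis discards 36% of the information on age. The documents do not support one figure. The loss could be as low as 14% with quartiles, or as low as 25% for a median split if age is uniform, and grouping loses nothing if risk truly steps at the chosen cut. This objection stands, and the size has to be given as a range.

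**A strong age effect would be found anyway.** This also stands. The 80% starting point is an assumption, and the gap nearly closes at a hazard ratio of 1.5 per SD.

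**Other tests may cover age.** Section 4.4 also compares baseline and follow-up parameters by t-test or signed rank test when they are continuous, without naming the groups. If this means dead against alive, age would stay continuous there. The wording is unclear, but such a comparison would ignore time to death and censoring. The grouped log-rank test remains the only time-to-event analysis of age.

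**Grouping has a use.** Kaplan-Meier curves need groups, and the log-rank test assumes no linear log-hazard. That supports keeping the curves; it does not support making the grouped test the only one.

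**The subgroup curves may be optional.** The word *eventually* in section 4.4 can be read as *possibly*. Birth date is kept, so a continuous analysis could be added later. That lowers the stakes, but if age is examined against survival, this is the method stated.

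**Conclusion.** The point holds as an inexpensive improvement to an exploratory analysis. With roughly normal age and a log-linear effect, information loss runs from about 14% (quartiles) to 46% (upper-quartile split). Power falls from an assumed 80% to between 54% and 61% across the four groupings examined. The loss is smaller if age is closer to uniform, larger if it is heavy-tailed, and of little practical consequence if the age effect is strong. The dependence on an unstated cut needs none of these assumptions.

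Three stronger readings are not supported:

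- **The primary result is weakened.** The estimate of three-year all-cause mortality does not use age groups.
- **The plan undercuts a declared aim of finding predictors of death.** Section 1 speaks of predictors of electrical storm, and section 2 states no hypothesis about age.
- **Ejection fraction and cycle length will be cut too.** Section 4.4 does not name them, and section 3.3 summarises echocardiographic parameters and cycle length by measures of centre and spread.

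**What to change.** Add to section 4.4: age, and any other continuous variable examined as a predictor of survival, will be tested in a Cox model on the continuous scale, with a spline check of linearity; for age, the hazard ratio per 10 years will be reported with its 95% CI. Keep Kaplan-Meier curves by age group for display, at cut points written into the plan before the data are analysed.

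The cost is a sentence or two of text and slightly more analysis work. No new data are needed, since birth date is already collected, and the software named in section 4.4 fits Cox models. The drawback is an assumed functional form, which the spline check addresses.

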2. AIM OF THE STUDY

The aim of the ELECTRA registry is twofold:

- a) To create an international registry on clinical features, optimal therapy, ablation strategy, prognosis and the effect of ICD programming on patients with ES.
- b) To use the data derived from the registry for a prospective, observational study on mortality and rehospitalization rate in patients with ES.

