4.1 PRIMARY ENDPOINT

- All-cause mortality 3 years after the ES

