4.2 SECONDARY ENDPOINT

- Hospitalization for all causes 3 years after the ES

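### Section 4.4 offers only Kaplan-Meier and gives no rule for deaths before a first admission; with deaths censored by default, the 3-year share hospitalized is overstated

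*Combined protocol and SAP*

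**What the plan says.** Section 2 states that the observational study concerns "mortality and rehospitalization rate in patients with ES", so hospitalization is one of its two named results. Section 4.1 makes the primary endpoint "All-cause mortality 3 years after the ES". Section 4.2 makes the secondary endpoint "Hospitalization for all causes 3 years after the ES", and death is not a component of it.

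Section 4.4 describes one time-to-event analysis: "Survival curves free from study endpoint", possibly split by subgroup, which "will be drawn with Kaplan-Meier method and compared by Log-rank test". It mentions no cumulative incidence function, no competing-risk method and no composite with death. It does not say how a patient who dies before any admission is handled.

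On mortality, section 4.4 assumes an "annual incidence of the primary endpoint (death from all causes) of 11" per cent. From this it projects about 55 deaths at one year and about 165 at three years.

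**The concern.** A patient who dies without having been admitted can no longer be hospitalized. Kaplan-Meier for hospitalization alone has no category for this patient other than censored. It therefore treats the patient as still able to be admitted later, at the same rate as the survivors. One minus the curve then estimates how many would be admitted if nobody died, which is not the share of patients who are admitted. The error is upward whenever some patients die before a first admission.

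By the plan's own figures death is common in this population, so the difference is not negligible. At stake is the absolute 3-year hospitalization figure, if it is read from the curves. Curves for subgroups that differ in mortality would likewise not show the shares hospitalized in those subgroups.

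**Working it through.** **Inputs from section 4.4.** 500 patients; 11% mortality a year; 3 years of follow-up.

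**Reproducing the plan's event counts.** 500 × 0.11 = 55 and 500 × 0.11 × 3 = 165. Both match the plan, and 165/500 = 33%. Compounding the yearly 11% gives 1 − 0.89³ = 29.5%, or 147.5 deaths. Reading 0.11 as a constant rate gives 1 − exp(−0.33) = 28.1%. Cumulative mortality at 3 years is thus roughly 30% on any of these.

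**Death hazard.** d = −ln(0.89) = 0.1165 a year.

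**Assumption not in the documents.** The first-admission hazard h is 0.15, 0.30 or 0.50 a year. Hazards are constant and independent.

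**Formulas at 3 years.**
- Kaplan-Meier with deaths censored: 1 − KM = 1 − exp(−3h)
- Share actually hospitalized (cumulative incidence): CIF = h/(h+d) × [1 − exp(−3(h+d))]
- Share dying before any admission: (d/h) × CIF

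**Worked case, h = 0.30.** 1 − KM = 1 − exp(−0.90) = 59.3%. With h + d = 0.4165, CIF = 0.7202 × 0.7134 = 51.4%. The difference is 8.0 points, or 40 of 500 patients.

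| h per year | 1 − KM | CIF | Overstatement | Of 500 | Die before admission |
|---|---|---|---|---|---|
| 0.15 | 36.2% | 31.0% | 5.3 points | 26 | 24% |
| 0.30 | 59.3% | 51.4% | 8.0 points | 40 | 20% |
| 0.50 | 77.7% | 68.3% | 9.3 points | 47 | 16% |

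(Differences are taken before rounding.)

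**Fewer deaths before admission.** If many deaths follow an admission, the relevant hazard is lower. With d/2 = 0.0583, CIF is 33.5%, 55.1% and 72.8%, and the overstatement is 2.8, 4.2 and 4.9 points.

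**More deaths.** If the plan's 33% at 3 years is taken literally, d = −ln(0.67)/3 = 0.1335. The overstatement is then 5.9, 9.0 and 10.6 points.

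**Check by simulation.** 400,000 simulated patients at d = 0.1165, with h set so that 1 − KM is 30%, 50% and 70%, gave 1 − KM of 30.0%, 49.9% and 70.0%. The shares actually hospitalized were 25.6%, 42.9% and 61.1%. The formulas give 25.6%, 43.0% and 61.1%.

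**The case against.** The strongest reply is that the plan nowhere says deaths are censored. Section 4.4 speaks of one study endpoint, directly after a sentence on the primary endpoint. If that endpoint is death alone, Kaplan-Meier is correct. If the phrase means alive and never hospitalized, Kaplan-Meier is again correct. The plan also does not say that the 3-year hospitalization figure will be read from the curve; a crude proportion or a rate per person-time would not carry this bias. All of this stands, and it makes the bias conditional on the default use of the method. It does not remove the gap. On the death-only reading the secondary endpoint has no time-to-event method, and the alive-and-not-hospitalized curve is not defined anywhere.

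A reader might also infer stronger things that the documents do not support:
- **That 30% mortality measures the bias.** Only deaths before a first admission matter, and these are 16% to 24% in the table above, or fewer if most deaths follow an admission.
- **That the log-rank test is wrong.** With deaths censored it validly compares cause-specific hazards. It simply does not compare shares hospitalized.
- **That curves for first ES, VT/VF or heart failure events are already affected.** These are data fields in Attachments #3 and #4. They are not endpoints, and no curves are planned for them.
- **That the bias in high-mortality subgroups can be stated.** It would be larger at the same admission hazard, but the documents give no subgroup mortality.

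Finally, section 3 calls the registry exploratory and this is a secondary endpoint. That limits the weight of the point but does not make the absolute figure right.

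**Conclusion.** The point holds in conditional form. The plan names one time-to-event method, has a secondary endpoint that excludes death, and sets no rule for death before admission. Used in its default way, the method overstates the 3-year share hospitalized by about 5 to 9 points, or about 3 to 5 points if death before a first admission is half as frequent. The direction is certain once deaths are censored and some precede an admission. The size rests on assumed admission hazards of 0.15 to 0.50 a year, constant independent hazards, and the plan's 11% annual mortality. A reader might take this as a demonstrated error in a planned result. The documents do not support that, because censoring of deaths is inferred and not written. The Kaplan-Meier analysis of all-cause death is sound. The change should be made, but it does not threaten the primary result.

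**What to change.** In section 4.4, keep Kaplan-Meier and the log-rank test for all-cause death. For first all-cause hospitalization, report the cumulative incidence function (Aalen-Johansen) with death as a competing event. Compare groups by Gray's test, or by a log-rank test explicitly labelled as comparing cause-specific hazards. Use the same approach for first ES, VT/VF or heart failure events only if curves are drawn for them.

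The text change is about two sentences, plus a routine that estimates cumulative incidence; its availability in the software named in section 4.4 should be confirmed. The reported hospitalization percentage will be lower than one minus Kaplan-Meier.

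There is also a data cost. The follow-up parts of Attachments #3 and #4 record heart failure rehospitalization, vital status and last follow-up date. They have no specific field for the date of first all-cause admission or the date of death. Those dates must come from the admission and vital-status reports in section 4.3, which should state that dates are required.

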3. REGISTRY DESIGN

The creation of the present registry is aimed at gathering information on a wide cohort of patients affected by ES. All patients will be enrolled for a minimum of three years from the protocol approval. There is no pre-specified date for the end of enrollment, which will be decided by the study responsible according to the enrollment rate.

A minimum of 500 patients will be included in the present registry. The exploratory nature intrinsic to the registry characteristics does not allow a sample size calculation by statistical means. However, the sample presented is based on the estimated enrolment rates of the participating centers during a 3-year enrolment period. Moreover, the sample size is large enough to postulate specific subgroup analyses.

REGISTRY INCLUSION CRITERIA:

- Diagnosis of ES (documentation of 3 or more episodes of sustained ventricular arrhythmia within 24h or documentation of sustained ventricular tachycardia lasted at least 12h). In order to fulfill this criterion, a patient with a previous episode of ES could also be enrolled during routine screening.
- Age ≥ 18
- Written informed consent

REGISTRY EXCLUSION CRITERIA:

- patient without ICD
- Confirmed or suspected use of drugs or narcotics with known direct pro-arrhythmic effect
- Inability to express an informed consent for the study

At enrollment, each patient will be informed on the aim and the design of the study, and the investigations needed. All patients that meet the inclusion criteria will be included in the study (attachment #1). All recruited patients will receive the informative form (attachment #1) and the informative letter to their general practitioner (attachment #2).

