
1.2 - Detection windows
 
VT detection rate  - VT if >24beats/12s  - ATP on VT  - Shock on VT  VT-1 detection rate (if present)  - VT-1 if >24beats/12s  - ATP on VT-1  - Shock on VT-1  VF detection rate  - VF if >24beats/12s  - ATP during charge 

2.1 - Electrical Storm
 
Electrical Storm geographical location  Electrical Storm start date  - Electrical Storm end date  - Electrical Storm beginning hour  Acute Coronary Syndrome as triggering ES event  - Acute Coronary Syndrome therapy  - ES triggering arrhythmias  Triggering arrhythmias cycle length  - Number of ATP delivered  - Number of shocks delivered  - Hospitalization length (days) 

2.2 - Previous arrhythmic events
 
Previous ES  - Previous VT/VF  - Previous VT ablation  - Previous inappropriate ICD therapies 

2.3 - ES medical management
 
Amiodarone  - Lidocaine  - Beta-blockers  - Sotalol  - Procainamide  Magnesium Sulfate  - Sedation  - Ablation  - CRT upgrade  - Pacing Overdrive  - Heart Transplant 

3.0 - ES ablation
 
Ablation date  - Ablation success  - Ablation number of attempts  - Ablation type  - Ventricular mapping  Endocardial approach  - Epicardial approach  - Electromechanical mapping  - Non contact mapping  - Irrigated tip catheters  Fluoroscopy time (min)  - Total procedure time (min) 

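### Section 4.4 gives the plan's only significance rule with the inequality reversed (p>0.05); almost certainly a typing error, corrected by one character

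*Combined protocol and SAP*

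**What the plan says.** Section 4.4 (Statistical analysis) plans two groups of tests. Survival curves, possibly split by sex, age, underlying heart disease, comorbidity and programming mode, "will be drawn with Kaplan-Meier method and compared by Log-rank test". Baseline and follow-up parameters are compared by chi-square or "by Fisher test if they are discrete; by T-student test or signed rank test if they are continuous".

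One sentence then sets the decision rule for all of them. It opens with "Every test will be two-tailed" and ends with "a value of $p>0.05$ will be considered significant".

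No other section gives a significance level or a rule for reading a p-value. Section 3 (Registry design) has none, because the sample size was not derived statistically: "The exploratory nature intrinsic to the registry characteristics does not allow a sample size calculation by statistical means". Section 3.3 (Data report) covers descriptive summaries only. The primary endpoint is itself reported descriptively: "The primary endpoint will be estimated annually and it will be expressed as absolute and relative numbers".

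**The concern.** A p-value is the probability, under the null hypothesis, of a result at least as extreme as the one observed, so significance is declared when it is small. The written rule declares it when the p-value is large. Because the sentence applies to every test, a literal reading swaps the significant and non-significant labels of every comparison in the plan. A subgroup difference in survival with p = 0.001 would be reported as not significant, and one with p = 0.80 as significant.

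What is at stake is the correctness of the written plan more than the likely conduct of the analysis. The reader has to supply the intended rule, since the documents state it nowhere else.

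**Working it through.** **Inputs, all from section 4.4 unless noted**
- Threshold 0.05, with significance assigned to values above it.
- Two-sided testing throughout.
- 500 patients, annual mortality 11%, and 55 and 165 expected deaths at one and three years.
- Basis of the 500: estimated enrolment rates (section 3), with no alpha, power or effect size.

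**The plan's own figures**
- One year: 500 × 0.11 = 55, which matches "we expect about 55 events at the first statistical analysis after one year from the start".
- Three years: 500 × 0.11 × 3 = 165, which also matches.

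Neither calculation uses a significance level, so neither changes when the sign is corrected. Reproducing 165 is not an endorsement of it. A constant 11% annual risk in a shrinking cohort gives 500 × (1 − 0.89³) = 147.5, which is a separate matter from the one raised here.

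**Error rate under the written rule**

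Under a true null hypothesis a continuous p-value is uniform on 0 to 1.
- Conventional rule: P(p < 0.05) = 0.05.
- Written rule: P(p > 0.05) = 1 − 0.05 = 0.95.
- Ratio: 0.95 / 0.05 = 19.

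For Fisher's exact test, which is conservative, P(p ≤ 0.05) is at most 0.05, so the literal rule labels at least 95% of true-null tests significant. The chi-square and signed-rank statistics are also discrete, so 95% is approximate for them.

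**The same rule on the test-statistic scale**

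The two-sided 5% critical value is |z| = 1.960, and 1.960² = 3.84, the 0.95 quantile of chi-square with 1 degree of freedom. For a two-group log-rank test or a 1-df chi-square test, the written rule therefore calls statistics below 3.84 significant and those above it not significant.

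These results need no assumed hazard ratio, group split or number of tests.

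**Could the sign be a conversion artefact?**

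Other inequality signs in the converted text read sensibly: the age criterion in section 3, and "VT if >24beats/12s" in the case report form (Attachment #3). They are weak evidence, because the p-value expression is set in mathematical mark-up and they are not. A misread is possible but not shown.

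**The case against.** The strongest reply is that this is proofreading and not a statistical problem. The intended rule is obvious from two-tailed testing and the conventional 0.05. Nobody would apply the literal version, so the 95% and 19-fold figures describe something that will not happen. The registry is exploratory, the primary estimate is descriptive, and the plan ties no confirmatory hypothesis or stopping rule to a p-value. The sign may also have been altered in conversion from PDF, in which case the plan itself is correct.

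Much of this stands. The expected practical effect is small, and the 95% and 19-fold figures measure only what the sentence says if taken literally, not likely harm to this study. Confidence is high that the available text reads p>0.05. That the original page reads the same still has to be confirmed.

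It does not remove the point. The sentence is the plan's decision rule, not background text, and no other section supplies the right one. Exploratory status explains why there is no power calculation, but section 4.4 still plans formal tests with a significance label, and that label is defined the wrong way round.

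**Conclusion.** The point holds. As the text stands, the only significance rule in the documents is reversed and covers every test in section 4.4. Taken literally, it would label about 95% of true-null comparisons significant instead of 5%. In practice the expected effect is small, on the assumption that the analyst uses p<0.05. No planned number changes: the 500 patients and the 55 and 165 expected deaths were not derived from alpha, and the primary endpoint is a descriptive estimate.

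This is a low-severity correction that should be made. It depends on the original page showing the same sign as the machine-read text. If that page already reads p<0.05, nothing needs to change.

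**What to change.** Check the sentence on the original page of section 4.4. If it reads p>0.05, replace > with <, so that two-sided p-values below 0.05 are the ones called significant. The cost is one character, with no new data, patients or analyses.

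An optional and separate clarification could be made at the same time: state whether baseline and follow-up parameters are compared within patients or between groups, and name tests to match. Between groups these would be chi-square or Fisher, unpaired t or rank-sum; within patients, McNemar, paired t or signed rank. This goes beyond the one-character correction and could change which tests are run, so it should be decided on its own merits.

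### The 165 expected deaths keep patients who have died at risk (about 141–148 at a constant 11%), and three-year mortality counted from the storm includes survival time that enrolment at consent guarantees

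*Combined protocol and SAP*

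**What the plan says.** **Expected events.** Section 4.4 starts from this rate: "Considering an annual incidence of the primary endpoint (death from all causes) of 11" (per cent). It then expects "about 55 events at the first statistical analysis after one year from the start", and for the full period "we expect about 165 events at the end of the follow-up of three years". Section 3 says that the 500 comes from expected enrolment at the centers over three years, not from a statistical calculation.

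**Endpoint and analysis set.** Section 4.1 defines the primary endpoint as "All-cause mortality 3 years after the ES". Section 4 takes its patients from the registry: "Data from the first 500 patients enrolled in the registry will be used for the present analysis". Section 4.4 reports the endpoint as counts and proportions, with survival curves that "will be drawn with Kaplan-Meier method and compared by Log-rank test".

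**Entry.** Section 3 requires written consent and excludes patients for "Inability to express an informed consent for the study". It also allows that "a patient with a previous episode of ES could also be enrolled during routine screening". Section 3.2 plans retrospective inclusion of patients whose ES came before the registry existed, provided among other things that they sign consent at their next routine visit. None of its conditions limits the time since the ES, except that the ICD must not have been replaced.

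**Dates.** The case report form (Attachment #3) has the start and end dates of the ES and the last follow-up date. Attachment #4 also asks for the last follow-up date. Neither lists a consent or enrolment date.

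**The concern.** There are two separate problems.

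The first is the event count. Death removes a patient from risk, so a constant yearly mortality cannot give the same number of deaths each year in a closed group. A total of exactly three times the first year suggests that this was overlooked. The 165 implies 33% three-year mortality, which the stated 11% does not support.

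The second matters more. The clock starts at the ES, but a patient can be enrolled only if alive at consent. The time between the two is therefore free of deaths by design. A standard Kaplan-Meier curve that counts patients at risk from the ES puts this time in the denominator, although no death in it could have been recorded. A patient whose ES was more than three years before consent can be one of the 500 and cannot have the primary endpoint at all. Three-year mortality is then biased downwards. Log-rank comparisons between subgroups are distorted if the subgroups differ in delay from ES to consent.

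**Working it through.** **Part 1: event count**

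Inputs: 500 patients (Sections 3, 4 and 4.4), 11% per year (Section 4.4), three years (Sections 4.1 and 4.4). Full follow-up and a constant 11% are assumed.

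1. The plan's figures: 500 × 0.11 = 55, and 55 × 3 = 165. Both reproduce exactly.
2. 11% as a yearly risk: 500 × 0.11 = 55.0; 445 × 0.11 = 48.95; 396.05 × 0.11 = 43.57. The total is 500 × (1 − 0.89³) = 147.5, or 29.5%. 165 / 147.5 = 1.119.
3. 11% as a person-year rate: 500 × (1 − e^(−0.33)) = 52.1 + 46.7 + 41.8 = 140.5 (the yearly terms are rounded), or 28.1%. 165 / 140.5 = 1.174.
4. Yearly risk needed for 165 deaths: 1 − (1 − 0.33)^(1/3) = 0.125, or 12.5%.
5. The 55 is right for each patient's first year under a yearly risk (52 under a rate). The plan does not say what its one-year point is measured from. On a calendar reading, with uniform accrual of 500 over three years (assumption), about 167 are enrolled by then. With h = −ln(0.89) = 0.1165, the expected count is 166.7 × [1 − 0.11/0.1165] ≈ 9 deaths.

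**Part 2: guaranteed survival time**

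The documents give neither the retrospective share nor the delay, so these are scenarios. They assume a constant 11% yearly risk (h as above; true three-year mortality 29.5%). Let v be the years from ES to consent.

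1. For a patient alive at v, the chance of dying within three years of the ES is 1 − e^(−h(3−v)).
2. Averaged over v uniform on 0 to a, this is 1 − [e^(−h(3−a)) − e^(−3h)]/(h·a). It equals 0.252 for a = 1 and 0.156 for a = 3.
3. Expected deaths in 500, and apparent mortality, when patients are counted from the ES and the remainder enter at the ES itself:

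| Retrospective share | Delay 0–1 year | Delay 0–3 years |
|---|---|---|
| 25% | 142.2 (28.4%) | 130.1 (26.0%) |
| 50% | 136.8 (27.4%) | 112.8 (22.6%) |
| 75% | 131.5 (26.3%) | 95.4 (19.1%) |

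4. Consent more than three years after the ES: if 50 of the 500 are such patients and the rest enter at the ES, 450 × 0.295 = 132.8 deaths (26.6%). That is 14.8 fewer deaths, or 2.95 points.
5. New patients only, all consenting 30 days after the ES: 1 − e^(−h × 2.918) = 28.8%. The apparent figure falls further below the truth if deaths cluster soon after the ES.
6. Check by simulation (4000 runs, 500 patients, half retrospective): counting from the ES gives 27.4% (0–1 year) and 22.5% (0–3 years). Delayed entry gives 29.5% in both.

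**Precision under delayed entry**

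The 95% half-width is 1.96 × S(T) × √(∫₀ᵀ h/n(t) dt), where n(t) is the number at risk. With half retrospective and new patients entering at the ES, the one-year half-width goes from 2.7 to 3.2 points (0–1 year) or 3.6 points (0–3 years). At three years it goes from 4.0 to 4.2 or 4.6 points.

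**The case against.** **The event count has no consequence.** This is largely true. The plan says about 165, and no test, stopping rule or sample size depends on it. The count would also follow if 11% were a three-year cumulative 33% divided by three. Section 4.4 does not say so, and an annual incidence reads against it. The correction stands as a minor one.

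**The size of the bias is unknown.** True. New patients may mostly consent during the index admission, since Section 3.1 screens admissions consecutively, and the retrospective share could be small. The scenarios rest on assumed shares and delays. The direction does not, and retrospective entry is planned.

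**The study is called prospective.** Sections 2 and 4 use that word, while Section 3.2 fills the registry partly with past cases and Section 4 takes the first 500. The sponsor may have meant to follow only new patients. The text does not restrict the 500 in that way, so the analysis set needs clarifying. Reporting new and retrospective patients separately would help, but new patients also enter only at consent, so it does not remove the problem.

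**Delayed entry may cost more precision than shown.** With half retrospective (0–3 years) and every new patient consenting at exactly day 30, a simulation gave a central 95% range of 6.9–22.0% at one year (true 11%) and 24.7–38.1% at three years (true 29.5%), because very few patients are at risk early on. With entry spread over days 0–30 the ranges stay close to the half-widths above. The caution is fair and is a reason to show numbers at risk.

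**The consent date may exist on the signed form.** Probably so, which makes the fix cheaper. It is still not among the data listed for collection.

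**Conclusion.** Both parts hold. The 165 is 12–17% too high for a constant 11%: about 148 deaths (29.5%) under a yearly risk or 141 (28.1%) under a person-year rate, against the implied 33%. Nothing in the design depends on it.

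The time-origin problem carries the weight. Followed as written, the plan understates three-year all-cause mortality, its primary endpoint. The direction follows from the entry rules. The size depends on figures that the documents do not give: over the scenarios examined, a true 29.5% would appear as anything from 28.8% to 19.1%. These assume a constant hazard, and the larger shortfalls exceed the roughly 4-point half-width of the study's own estimate.

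**What to change.** **Event count.** In Section 4.4, replace 165 with about 141–148 deaths over three years. State whether 11% is a yearly risk (148, with 55 in year one) or a person-year rate (141, with 52 in year one), and that the one-year point is in per-patient time. Add that fewer deaths will be seen within three years of the ES if many patients enter late.

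**Primary analysis.**
- Record the consent date for every patient, retrospective or new.
- Keep time since the ES as the time scale, and count each patient at risk only from consent, in both the Kaplan-Meier curves and the log-rank tests.
- Report mortality at 1, 2 and 3 years after the ES with 95% confidence intervals and numbers at risk, so that thin early risk sets are visible.
- Report how many of the 500 consented more than three years after the ES. They contribute nothing to this endpoint.
- State that deaths before consent are not observed, and that delayed entry assumes that the timing of consent is unrelated to the risk of death.
- Say whether retrospective patients belong in the study that Section 4 calls prospective. If they do, also show new and retrospective patients separately.

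**Cost.** One date field, a check that the planned software handles delayed entry, and some precision, mostly early in the curve. The loss is modest if many new patients consent soon after the ES, and larger if few do. No extra patients or visits are needed.
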